Research has shown that a successful implementation depends on interplay between the effectiveness of the implementation strategies chosen to support the implementation and characteristics of the implementation object, the implementers, the target population and the context of the implementation (Table 1).

Updated design of the implementation research

The project was planned to be conducted using a cross-over design in two counties in south of Sweden based on a feasibility/pilot study that was conducted during fall 2014 *co-created palliative care educational intervention through seminars for professionals in nursing homes*. Due to a more significant amount of drop-outs compared with expected (and for not receiving the total amount of applied foundation), the plan needed to be revised. The knowledge-based palliative care intervention was conducted as a non-randomized control trial, implemented over a six-month period in 30 nursing homes in two different counties in the south of Sweden (County A and County B). The data collection was made in two sequential periods in each county. First, the intervention was implemented in ten nursing homes in County A (Kronoberg County from April 2015), while ten nursing homes in County B served as a control group. Then, County B implemented the intervention (Skåne county from August 2016), and ten new nursing homes in County A, which had not received the intervention, were chosen as a control group. After the two sequential time periods were data from one intervention and one control group analysed. The selection through voluntary participation resulted in a mixture of both larger and smaller nursing homes within the two counties (cluster samples), as well as both from urban and rural areas.

Implementation object

According to the National Board of Health and Welfare, palliative care should be based on four cornerstones: symptoms relief, multi-professional cooperation, communication and relation as well as support to the next of kin (Socialstyrelsen 2012). The aim of palliative care is to reduce suffering and promote the quality of life for patients with progressive, incurable illnesses or injuries. The care should address physical, psychosocial and spiritual needs as well as provide support to the next of kin. The definition by the National Board of Health and Welfare closely

adheres to the definition of palliative care by the World Health Organization (WHO), (Socialstyrelsen 2013).

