Implementation intervention/strategies

The educational strategies will be based on *co-created palliative care educational intervention*, which consists of a series of seminars and coaching. The education has been planned together with staff, informal caregivers and patients. The educational material for use in the seminars has been developed as well as empirically tested in the feasibility study during the fall 2014. The strategies were tested in this feasibility study at four nursing homes in Kronoberg County during the autumn 2014, in order to understand how the implementation object can be translated into practice at nursing homes. Seven educational meetings were reduced to five as a result of the study.

Every seminar group meeting once a month includes different professions (unit manager, district nurse, assistant nurse, and other staff i.e. occupational therapist and physiotherapist). There will be 5 meetings with 8-10 participants in each group from each nursing home. The total intervention period is 6 months in each nursing home.

The educational strategies are based on the two national knowledge documents concerning palliative care in the end of life and the Swedish Register of Palliative Care (SRPC). The educational binder was developed based on the content in the two national knowledge documents and is used in this intervention. Each participant is provided a binder at the beginning of the intervention. The educational material consists of six themes; values in palliative care, symptom relief, dignity and a dignified death, collaborative co-creating care, support to next of kin and dialogue with older persons and next of kin about death and dying. The content of the different themes will have a common core for each nursing home but will be adjusted based on the expressed needs of each nursing home. In addition, there will be a list of references available for further self-studying by the participants.

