The seminar groups will be led by two experienced clinical nurses and researchers from the field of palliative care and geriatric care. The participants in the seminar groups will reflect together over the content of the developed binder of educational material and will relate it to their own work in order to identify areas suitable for changes and/or development. These areas will also be identified based on the Swedish Register of Palliative Care (SRPC). The knowledgebase for discussions in the seminar groups is seven selected quality indicators out of the total of 27 questions concerning essential aspects of palliative care. The seven quality indicators are: Prevalence of pressure ulcers, documented individual prescription when needed of opioid and anti-anxiety drugs, oral health assessment, talks about the substance and direction, pain analysis and regular estimation of pain intensity and regular use of instrument for symptom assessments.

The evaluation of the implementation

Data collection is made before and after the implementation, same time for intervention- and control groups. The implementation of the educational intervention will be evaluated by using qualitative and quantitative methods (see Table 2).

Table 2. Sub studies and data collection i Kronoberg County and Skåne County 2015 and 2016 for the implementation of knowledge based palliative care.

Subjects	Method	Selection in the implementation nursing homes	Selection in the control nursing homes*
Sub study 1: Older persons	Structured interview (based on WHOQOL-BREF (26 items), WHOQOL-OLD (24 items), P-CAT (13 items) and The Person-Centered Climate Questionnaire (17 items)	20 older persons were interviewed before and after three months after finished implementation	The same as for the implementation nursing homes
Sub study 2: Next of kin	Qualitative interviews participation and structured interview WHOQOL-BREF (26 items), WHOQOL-OLD (24 items)	20 next of kin before and three months after finished implementation	20 next of kin before and three months after finished implementation
Sub study 3: Next of kin	The participation of next of kin in palliative care at nursing homes (36 items) WHOQOL-BREF (26 items), WHOQOL-OLD (24 items)	100 next of kin before and after nine months	100 next of kin before and after nine months
Sub-study 4:	Psychometric study; test-retest, explorative factor analysis	See above	See above

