Sub study 5: Staff	Focus group interviews (preparedness for implementation)	20 staff divided into 3 groups before and after the implementation is finished	
Sub study 6: Staff	Questionnaires at two occasions: Experiences of palliative care (46 items), P-CAT (13 items) and the Person-Centered Climate Questionnaire (14 items)	100 staff before and after the implementation is finished	100 staff with 6 months in between
Sub study 7: Managers	Two individual interviews with managers (organic preparedness for implementation)	20 managers at different levels-, during the intervention and after six months	
Sub study 8: Implementation context	An ethnographic study: Observations and qualitative interviews	Observations on 28 occasions at 7 nursing homes with a strategic selection of qualitative interviews during the implementation	

THE OVERALL AND SPECIFIC AIMS

The overall aim of this research project is to evaluate the outcomes and effectiveness of the implementation method of a knowledge-based model for palliative care in nursing homes. The overall aim can be broken down into four specific research questions and nine different studies:

1. What is the outcome of the implementation intervention in terms of quality of life, participation and quality of care in older persons and next of kin at nursing homes before and after? (Study I, II-IV)
2. Investigates the staff's implementation process of palliative care and the role of the leadership and (Study V-IX).
3. Investigate which factors (barriers and facilitators) that affect the implementation process of this model (Study V, VII-IX).

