The evaluation consist of 8 studies and involves four implementation outcomes in accordance with the framework proposed by Proctor *et al.* (2011): **Acceptability** - The perception among implementers (nursing home staff and managers) that a given knowledge-based practice (palliative care in nursing homes) is agreeable, towards benefit or satisfactory; **Appropriateness** - The perceived fit, relevance or compatibility of an knowledge-based practice (palliative care), for a given practice setting, provider, or consumer (older persons and their next of kin); **Feasibility** - The extent to which an knowledge-based practice (palliative care) can be successfully used or carried out within a given agency or setting (nursing homes); and **Fidelity** - The degree to which an knowledge-based practice (palliative care in nursing homes) was implemented as it was prescribed in the original protocol (the knowledge documents concerning palliative care).

Participants in studies

The persons asked for participation in this study, i.e. older persons, next of kin, staff and leaders are recruited from the included nursing homes in both Skåne and Kronoberg counties. The persons are selected consecutively until the stipulated figures are reached (Table 2).

Methods and instruments

The following methods and instruments will be used in this project:

Questionnaires

Quality of life: The WHOQOL-BREF questionnaire (WHO, Manual 1996) and the WHOQOL-OLD questionnaire (WHO, Manual 2006) assessed quality of life. The older persons and next of kin will answer to the questions in a structured interview. The WHOQOL-BREF is often used together with the WHOQOL-OLD module and both are psychometric tested by the WHOQOL Group (Power *et al.*, 1999). The WHOQOL-OLD module have been validated for old people in several countries, for example Sweden (Power *et al.* 2005) and can be used in a wide variety of studies including cross cultural investigations, population epidemiology, health monitoring, service development, and clinical intervention trials in which issues about quality of life are crucial (WHO, Manual 2006). The project has acquired permissions from WHO to use these questionnaires and in order to make it easier to answer the questionnaires, the answer alternatives will be enlarged on a separate paper and used during the interview.

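### Recruiting consecutively to a group total, with no limit per home, permits the sample to concentrate in a few nursing homes and lose precision and balance

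*Protocol*

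**What the plan says.** Under Participants in studies, the protocol says that older persons, next of kin, staff and leaders "are recruited from the included nursing homes in both Skåne and Kronoberg counties", and then: "The persons are selected consecutively until the stipulated figures are reached (Table 2").

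Table 2 gives one figure per group of homes. For the implementation homes these are:
- Sub study 1: "20 older persons were interviewed before and after three months after finished implementation"
- Sub study 3: "100 next of kin before and after nine months"
- Sub study 6: "100 staff before and after the implementation is finished"

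The control homes have the same numbers. No minimum, maximum, quota or stratification by home appears in either document.

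The only figure tied to a single home is in the section on implementation strategies: "There will be 5 meetings with 8-10 participants in each group from each nursing home". That describes seminar attendance, not who completes the outcome questionnaires.

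On the homes themselves, the updated design section says: "The selection through voluntary participation resulted in a mixture of both larger and smaller nursing homes within the two counties (cluster samples"). It adds that they come from both urban and rural areas.

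**The concern.** The education is delivered to homes, and its content is adapted to each home's needs. Several outcomes also describe the home: the P-CAT and the Person-Centered Climate Questionnaire rate the care setting, so people rating the same home are likely to give similar answers. Information about the intervention then depends on how many homes contribute and how evenly, as well as on the number of people.

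A rule that stops at a group total controls neither. Large homes have more eligible people and can fill the total sooner, leaving small homes with few participants or none. Two things are at stake:
- **Precision.** The same number of people from fewer homes carries less information whenever the intracluster correlation (ICC) is above zero.
- **Balance.** The trial is non-randomised with volunteer homes. If filling differs between arms, they can differ in home size and urban or rural setting for reasons unrelated to the education.

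**Working it through.** **Plan's own figure.** Neither document derives the Table 2 totals. No power, effect size, standard deviation, ICC or drop-out rate is given, so there is no calculation to reproduce.

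**Number of homes.** The updated design section has the intervention "implemented over a six-month period in 30 nursing homes in two different counties in the south of Sweden". Each period has ten intervention and ten control homes, and the County B homes are controls first and intervention homes second. Counting a home once per period in which it takes part, each arm has 10 × 2 = 20 home-periods.

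**Unit of the Table 2 figures.** Table 2 covers both counties and both years without saying whether a figure is per arm and period or pooled.
- Per arm and period: the total is spread over 10 homes, so equal shares are 20/10 = 2 older persons, 100/10 = 10 next of kin and 10 staff per home.
- Pooled per arm: the total is spread over 20 home-periods, so equal shares are 1, 5 and 5.

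The protocol says that the next-of-kin questionnaire was tested on 400 people. This equals 100 × 2 arms × 2 periods and hints at the first reading, but does not settle it.

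**Effective sample size.** For n people in equal groups of m per home, design effect = 1 + (m − 1) × ICC and effective n = n / design effect. The four-home split and the ICCs are assumptions. The outcome is taken as measured once.

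| Assumed ICC | Ten homes, m = 10 | Four homes, m = 25 | Loss |
|---|---|---|---|
| 0.02 | 100/1.18 = 85 | 100/1.48 = 68 | 1 − 1.18/1.48 = 20% |
| 0.05 | 100/1.45 = 69 | 100/2.20 = 45 | 1 − 1.45/2.20 = 34% |
| 0.10 | 100/1.90 = 53 | 100/3.40 = 29 | 1 − 1.90/3.40 = 44% |

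Under the pooled reading, the even benchmark is 20 home-periods of 5. Effective n is then 100/1.08 = 93, 100/1.20 = 83 and 100/1.40 = 71 at the same three ICCs.

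**Uneven filling without empty homes.** With unequal groups, m is replaced by Σm²/Σm. For an assumed split of 40, 20, 10, 5, 5, 5, 5, 4, 3 and 3, Σm²/Σm = 2234/100 = 22.34. At ICC 0.05 the design effect is 1 + 21.34 × 0.05 = 2.07 and effective n is 48, against 69 when even.

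**Target of 20.** At ICC 0.05, ten homes of 2 give 20/1.05 = 19.0, and two homes of 10 give 20/1.45 = 13.8.

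**Degrees of freedom.** A comparison of arms based on homes has about 2 × (k − 1) degrees of freedom for k homes per arm: 18 with ten homes, 6 with four. This cost of few homes comes on top of the loss in effective n.

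**The case against.** The strongest reply is that the harm is a scenario. No count per home is reported, nothing says that any home contributed nobody, and both the ICCs and the four-home split are assumed. This stands: the documents show a permitted risk and no more. The mark on the control column of Table 2 also refers to a note that is not in the available text, and that note may bear on selection.

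Second, the calculation does not match the planned tests. The SAP's comparative section analyses questionnaires within each group by the Wilcoxon signed rank test on before and after data. Stable differences between homes largely cancel in change scores, so the relevant quantity is the ICC of change, which could be smaller or larger. This also stands, and a reader should not take 20% to 44% as the loss in the planned analysis. The SAP does compare arms in one place, the univariate logistic regression on staff improvement. Like the other tests, it has no term for home, a separate weakness that quotas would not cure.

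Third, a reader might infer that homes starting early would fill the sample. The protocol gives one start date per county, says that data collection was simultaneous in the intervention and control groups, and describes no staggered start within a county. Only home size is supported as a driver.

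For staff, the implementers are described as all staff at the included homes, with seminar groups from each. This makes a four-home staff sample less likely, but sets no quota for the survey.

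Finally, recruitment is over, so a quota cannot change it. That shapes the remedy but does not remove the point.

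**Conclusion.** The concern holds as a weakness of the recruitment rule. Selection stops at a group total, no number per home is set, and the homes are acknowledged clusters of unequal size. The rule therefore permits concentration in a few homes. For any ICC above zero this lowers precision, and it can unbalance home size and setting between arms.

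The size is illustrative: effective n falls from 85 to 68 at ICC 0.02 and from 53 to 29 at ICC 0.10 when 100 people come from four homes instead of ten. This rests on the assumed ICCs, an assumed equal split and a single-occasion outcome. For the planned before/after changes the documents do not allow a figure.

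A reader might also infer that homes were in fact left out, or that the arms did become unbalanced. The documents report nothing from which either could be judged.

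**What to change.** 1. **State the unit.** Say for each Table 2 figure whether it is per arm and period or pooled over both periods.
2. **Set a quota or cap per home**, for any repeat or extension of the study. Recruit consecutively within each home up to the Table 2 total divided by the number of contributing homes, and release unfilled places to other homes only after a set date. The figures for older persons, next of kin and staff are 2, 10 and 10 with ten homes, or about 1, 5 and 5 with 20 home-periods. The unit must be settled first: 2, 10 and 10 applied to 20 home-periods would give 40, 200 and 200 per arm, twice the totals if those are pooled.
3. **For data already collected**, report participants by home, arm and period, and describe the size and setting of the contributing homes in each arm. Compare arms with a home-level analysis of change or a model with home as a random effect, treating the County B homes as the same homes in both periods. Check whether the result depends on any one dominant home.

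**Cost.** The quota needs one protocol sentence and a recruitment log per home, and no extra participants if it adds up to the stated total. Small homes will fill more slowly and be somewhat over-weighted relative to their residents and staff. With one or two older persons per home, drop-out, which the protocol reports as higher than expected, could leave some homes without follow-up. The third step needs only each participant's home identifier and additional analysis.

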Official title of the study:
Implementation of Knowledge-Based Palliative
Care for Frail Older Persons in Nursing Homes

NCT number: NCT02708498

Date of the document: April 8, 2015, updated October 6, 2020

Statistical Analysis Plan

Simple descriptive statistics:

Median-Mean, Quartiles, Percentage

These are applied to all quantitative studies.

Baseline study:

Target population: Older people

Instruments: Characteristics of older participants, WHOQOL-BREF & WHOQOL-OLD

The data were analysed in one descriptive and one analytical section. In the descriptive section, numbers and percentages were calculated on a group level. A mean score was calculated for each domain using both the raw domain score, a standardized domain score (SDS) with the raw domain score divided by the number of items in the domain (1-5) and a transformed domain mean score (TDS 0-100) according to the instrument manuals. The different calculations were performed to enable comparison of our results with those from other studies.

In the analytical section, the participants were divided into two age groups (66-88 years and 89-102 years) by the population median age and gender (female and male). To examine differences in quality of life, a comparison of medians was conducted using the Mann-Whitney U test.

Comparative studies (Baseline and Follow-up):

Target population: Older people, next-of-kin, staff

Instruments: PCAT, PCQ-S, PCQ-P, WHOQOL-BREF, WHOQOL-OLD, Your experience of palliative care, Next-of-Kin Participation in Care (NoK-PIC)

The selection of the statistical tests to analyze data other than the descriptive statistics was based on whether the data were distributed normally and the scale level of the instruments. The Mann-Whitney U-test and the Kruskal-Wallis test was applied to compare the baseline characteristics of the two groups. The quantitative data collected from questionnaires were analyzed using within-group comparisons (the data from after the intervention period were compared with the data from before the intervention period in the intervention group and the control group) by Wilcoxon signed rank test.

Either Pearson's chi-square test or Fisher's exact test was used when the expected value was less than 5.

A two-tailed p-value of <0.05 was regarded as statistically significant.

In order to investigate if the drop-outs consisted a threaten of external validity we performed sub-groups analysis through comparing the drop-outs in the intervention group with the participants in the intervention group, and comparing the drop-outs within the control group with the participants in the control group.

Analyses were performed using IBM SPSS Statistics version 24.

Logistic regression studies (Baseline and Follow-up):

Target population: Staff
Instruments: P-CAT, PCQ-S

A univariate logistic regression analysis was performed with the independent variable improvement/non-improvement in P-CAT and PCQ-S and the dependent variable group (control/implementation).

Psychometric studies

Target population: Next-of-kin
Instrument: Next-of-Kin Participation in Care (NoK-PiC)

Step 1. Dimensionality

The dimensionality of the 37 items was explored by means of Rasch Model Analysis (RMA) and Explorative Factor Analysis (EFA). EFA needs complete data, i.e. no missing responses in any items. RMA can process missing data. Estimation methods merely summarize the non-missing observations that are relevant, and compare them with their expectations.

NoK-PiC data was analysed according to Rasch Measurement Theory (RMT), using the polythomous Rasch model in RUMM2030 (Professional Edition 5.4). A principal component analysis of the residuals was conducted in RUMM2030 to explore dimensionality of the NoK-PiC items. Person location estimates were derived from subsets of items that loaded positively and negatively on the first principal component of residuals. The overall proportion of persons with significantly different measures from the two item subsets should be <5% to support unidimensionality.

EFA was conducted based on recommendations including parallel analysis to decide for decision about how many factors to retain for rotation, Minimum Rank Factor Analysis (MRFA, that is able to estimate the percentage of common variance explained by the EFA model), and on a promine rotation that allows factors to correlate (oblique). In addition, since the items are polythomous, and since MRFA assume only minor departures from normality, we based the analysis on a polychoric correlation matrix. The software FACTOR (Lorenzo-Seva, Ferrando, release 10.5.03, June 2017) was used to conduct EFA.

Step 2. Item reduction

Based on conceptual reasoning among the researchers and based on RMA item reduction was conducted. The main statistical reasons for item reduction was based on item fit. In general, individual item fit residuals should range between -2.5 and 2.5, with the ideal being 0. Signs of multidimensionality/under discriminating items (fit residuals >2.5) and local dependency/item redundancy/over discriminating items (fit residuals > -2.5) led to further exploration of the possible reasons for misfit. This exploration included inspection of item residual correlations, and the item characteristic curves to get a graphical understanding of the deviations from Rasch model expectations. The nature of observed misfit (local response dependence or multidimensionality) often needs to be determined based on conceptual reasoning rather than statistics.

Step 3. Dimensionality after item reduction

Dimensionality of the remaining 30 items (after step 2) was explored using EFA, following the same procedures as described above (Step 1). The appropriateness of performing EFA was, in this step, checked according to quality criteria, i.e. by means of: the Kaiser-Meyer-Olkin Measure of Sampling Adequacy (should be KMO 0.50 or above); and Bartlett's test (should be p-value <0.05).

Step 4. RMA of final and separate factors

According to RMA, a set of items, supposed to be unidimensional, rated (dichotomous or polytomous scoring) in a sample, are compared to the "Perfect Rasch Model" that is based on fundamental measurement principles from the physical sciences. The model separately locates persons and items on a common interval level logit metric, ranging from minus to plus infinity, with mean location set at zero. The extent to which a successful measurement has been achieved is determined by examining the fit between observed data and model expectations. If data accord sufficiently with the model, linear measurement and invariant comparisons are possible. However, almost no scale is perfect, thus "almost perfect" can be a goal to achieve. Here the RMA addresses targeting, reliability, model fit, Differential Item Functioning (DIF, by gender and age), and hierarchical item ordering.

Step 5. Group comparisons

The IBM SPSS Statistics 23 software was used for comparisons between independent groups. Data were assessed regarding underpinning assumptions, described, and analysed using Mann Whitney U-tests. Significance was set to $P < 0.05$.

Target population: Next-of-kin

Instrument: WHOQOL-BREF

Data were analyzed using IBM SPSS Statistics 20 and IBM SPSS Amos, version 25. In a first step, WHOQOL-BREF's negatively phrased items (Q3, Q4, and Q25) were reversed (1=5, 2=4, 3=3, 4=2, 5=1). Two items – question 1, about overall QOL, and question 2, about the overall perception of health – were analyzed separately.

Validity

Internal validity in terms of data quality and targeting was assessed by missing values, item response, and floor and ceiling effects. Floor and ceiling effects were calculated and should be less than 20% in order to ensure that the scale is capturing the full range of potential responses in the population and that changes over time can be detected. The Kolmogorov-Smirnov test was used to assess normality at the item level. A statistically non-significant result ($p \geq 0.05$) indicates normality. Construct validity was estimated by correlating item/question 1: "How would you rate your QOL?" and item/question 2: "How satisfied are you with your health?" with the four domains in the WHOQOL-BREF using Spearman's rank correlation.

Reliability

Internal consistency was assessed using Cronbach's alpha. To determine to which degree each item correlates with the total score, Corrected Item-Total Correlations (CIT) were calculated. The limit for satisfactory item correlation was set to > 0.30 . Values less than 0.30 indicate that the item is measuring something different from the scale as a whole.

Factor structure

The appropriateness of performing CFA was checked according to quality criteria. These criteria were fulfilled by means of the Kaiser-Meyer-Olkin Measure of Sampling Adequacy (0.90, should be 0.50 or above); Bartlett's test (0.01, should be < 0.05); and determinant (0.008, should be > 0.00001). The number of cases per item was also calculated. Recommendations range from 2 to 20 subjects per item, with an absolute minimum of 100 to 250 subjects. Confirmatory Factor Analysis (CFA) was applied to assess goodness of fit by means of various descriptive fit indices. Specifically, the normed fit index (NFI), the comparative fit index (CFI) and the root mean squared error of approximation (RMSEA) were used.

The NFI equals the difference between the chi-square of the two models divided by the chi-square of the null model. An NFI over 0.90 is preferable. An NFI of .90 shows that the model of interest improves the fit by 90% in relation to the null model. CFI assesses fit relative to a null model and ranges from 0 to 1, where values exceeding 0.95 are regarded as acceptable. The RMSEA test assesses the lack of fit per degree of freedom of the model. Zero represents a perfect fit, ≤ 0.05 indicates very good fit, $>0.05-0.08$ good fit, and ≥ 0.10 poor fit. IBM SPSS Amos only accepts data files with no missing values, and therefore, 14 participants were excluded from the CFA analysis (n=240).

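### The SAP's baseline study calls the Mann-Whitney U test a comparison of medians without an equal-shape condition, and plans no between-group estimate with a confidence interval

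*SAP*

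**What the plan says.** The baseline study concerns older people and the WHOQOL-BREF and WHOQOL-OLD. Its descriptive part calculates mean domain scores on three scales: the raw score, the raw score divided by the number of items (1-5), and a transformed score (TDS, 0-100). The purpose given is comparison with other studies.

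Its analytical part splits the participants at the median age (66-88 and 89-102 years) and by gender, and then says: "To examine differences in quality of life, a comparison of medians was conducted using the Mann-Whitney U test". Nothing further is planned there: no measure of the difference, no interval, and no condition on the distributions.

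Three other places bear on the point:

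- The SAP opens, under Simple descriptive statistics, with "Median-Mean, Quartiles, Percentage" and adds "These are applied to all quantitative studies". Medians and quartiles are therefore planned for the baseline study as well as means.
- Under Comparative studies, test choice depends on normality and scale level, and the threshold is given: "A two-tailed p-value of <0.05 was regarded as statistically significant". I assume that this threshold also applies to the baseline study.
- In the NoK-PiC psychometric study, Step 5 says that assumptions were assessed before Mann-Whitney tests were run. The baseline study has no such sentence.

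**The concern.** The Mann-Whitney test and a comparison of medians answer different questions unless the two score distributions differ only in location. Domain scores are bounded, and nothing in the plan makes their shape or spread equal between women and men or between the two age groups. As the SAP words it, p<0.05 will be read as showing that median quality of life differs, and the test by itself does not establish that.

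The second half of the point is the missing estimate. The age and gender comparison is the only inferential analysis named for this study. The SAP calculates a 0-100 score so that results can be set beside other studies, yet it plans no between-group contrast on that scale and no interval on any scale. A reader would have a p-value without a stated size of difference or its uncertainty.

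**Working it through.** **Inputs.** The documents state no sample size, SD, effect or result for this comparison, so there is no figure of theirs to reproduce. The nearest count is in Protocol Table 2, sub study 1 ("20 older persons were interviewed before and after three months after finished implementation"), which does not give the sizes of the age or gender groups. All group sizes and shapes below are assumptions.

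**What the test measures.** Let θ = P(X>Y) + ½P(X=Y). The statistic U/(n1·n2) estimates θ, and the test looks for departure from 0.5.

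- If Y has the distribution of X moved by Δ, the difference in medians and the difference in means both equal Δ. A significant result then supports both.
- If shapes differ, θ can differ from 0.5 while the medians are equal.

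**First simulation.** Two-sided asymptotic test at 0.05, 4,000 runs per cell. Scores are centred at 80. The skewed shape is gamma (shape 1.5, scale 10; median 11.8, mean 15.0, SD 12.2), reflected for left skew. The symmetric shape is normal, SD 12.2. Scores are continuous and not confined to 0-100. The Monte Carlo standard error at 5% is √(0.05×0.95/4000) = 0.3 percentage points. Rejection rates in percent:

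| n1/n2 | Identical | Equal medians, left-skewed v normal | Equal medians, normal, SD 12.2 v 36 | Equal medians, opposite skew | Same shape, shifted 6.1 (0.5 SD) |
|---|---|---|---|---|---|
| 10/10 | 4.0 | 5.3 | 6.1 | 7.4 | 26.5 |
| 20/20 | 4.7 | 7.7 | 7.2 | 14.1 | 48.5 |
| 50/50 | 5.4 | 11.9 | 7.1 | 28.3 | 87.6 |
| 100/100 | 4.8 | 18.4 | 7.5 | 50.0 | 99.2 |
| 140/60 | 4.9 | 18.4 | 10.7 | 43.3 | 97.1 |

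In the left-skewed v normal case both medians are 80, but P(X>Y) is 0.455 and the means differ by 15.0 − 11.8 = 3.2 points. The rate rises with n because the test is detecting a real difference that is not a difference in medians. With those two shapes set to equal means instead, the rates are 5.1%, 6.7%, 8.7%, 12.6% and 12.3% down the rows.

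**Second simulation.** A discrete score from 3 to 15 with both medians at 11, 3,000 runs. The test rejects in 9.7% at 56 v 24 when the smaller group has twice the SD, and in 7-11% for left-skewed v symmetric groups (total n 80-120). It stays at 5% when shapes are equal. Opposite skew gives 16-27%.

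**Which rows apply.** A split at the median age gives two age groups of roughly equal size. The unequal-size scenarios therefore bear mainly on the gender comparison.

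**A side result.** In the SD 12.2 v 36 column θ is exactly 0.5, yet 10.7% reject at 140/60. With unequal spread and unequal group sizes, the ordinary p-value is not exact even for the hypothesis θ = 0.5. This affects how the interval should be computed.

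**The case against.** The case against giving this much weight is substantial, and most of it stands.

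- A rank test is an accepted choice for bounded, ordinal-type scores. It is valid for its own null hypothesis: 4.0-5.4% rejection with identical distributions.
- A reader might infer that a significant result supports neither a median nor a mean difference. That goes too far. Under a location shift it supports both, and the defect is an unstated condition.
- A reader might infer that only means are reported, or that no size will be visible at all. The opening section plans medians, means and quartiles for every quantitative study. The SAP does not say that they will be tabulated by age and gender, but it does not exclude it. What is clearly absent is a planned contrast with an interval.
- The high rates under opposite skew (16-27% and up to 50%) should not be used as the size of the problem. Nothing in the documents suggests that women and men, or the two age groups, are skewed in opposite directions.
- The rejections under different skew are largely not false alarms about the scores. In a further check on a 3-15 score with equal medians and assumed shapes, opposite skew at 40/40 gave 13% rejection for Mann-Whitney and 31% for Welch's test of means. Left-skewed v symmetric at 60/60 gave 15% and 31%. The distributions really differ, so these rates count only against the word medians.
- In the same check, roughly doubled spread mattered mainly with unequal groups: 9.9% at 56/24, but about 6% at 40/40 and 60/60.
- A reader might infer that the rank test should give way to a comparison of means. That would change the quantity being estimated, and the documents give no reason to require it.

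None of this supplies the missing condition or the missing interval.

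**Conclusion.** The point holds as a minor one. The baseline section attaches an inference about medians to a test that supports it only under an unstated and unchecked condition, and it plans no between-group estimate with an interval. Without equal shapes, a significant result indicates that one group tends to score higher, and does not by itself show that the medians differ.

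Under the assumed moderate departures, the test rejects with equal medians in about 5-18% of runs (7-11% on the discrete score), against about 5% with equal shapes. These figures depend wholly on assumed shapes and group sizes, and they show direction rather than what happened in this trial.

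The consequence is limited. This is a cross-sectional age and gender description at baseline. It does not estimate the effect of the intervention, and it gives no ground for doubting the before-after analyses under Comparative studies.

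**What to change.** In the SAP, Baseline study:

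1. Keep the Mann-Whitney test, delete the description of it as comparing medians, and call it a test of whether one group tends to score higher.
2. For each domain, and for both the age and the gender comparison, report P(X>Y) with ties counted half and a 95% CI. Use a method that does not assume equal shapes, such as Brunner-Munzel. Dividing the raw score by the number of items does not alter ranks, so this measure is the same on the raw and 1-5 scales. It is also the same on the TDS if that transformation is increasing.
3. Alternatively, report a Hodges-Lehmann shift on the TDS 0-100 scale with a 95% CI, and state that it assumes equal shapes.
4. Tabulate group medians and means by age group and by gender beside the estimate.
5. A Welch difference in mean TDS with a 95% CI may be added as a supplement. It need not replace the rank test.

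The cost is a wording change and a small re-analysis of baseline data. The SAP describes this analysis in the past tense, so any report that already speaks of median differences would need the same rewording.
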